6.7.2 Secondary Efficacy Endpoints

All secondary efficacy analyses will be conducted using the ITT population

6.7.2.1 Health Economic Summary

Health economic parameters will be evaluated and include the following:

• Duration of hospital stay post-surgery = Date of discharge from hospital – Date of surgery completion + 1

| Statistical Analysis Plan | | Pa | ge 14 of 19 |
|--|-------|-----|-------------|
| Sponsor | Study | | Version |
| CytoSorb [®] REduction of FREe Hemoglobin/Acute Kidney Injury (AKI) during Cardiac Surgery | | 1.0 | |

- Duration of ICU stay post-surgery = Date of discharge from ICU Date of admission to ICU/date of surgery completion + 1
- Duration of renal replacement therapy post-surgery= End date of therapy Start date of therapy (post-surgery) + 1
- Rate of vasopressor medication use post-surgery
- Duration of ventilator use post-surgery = Ventilation end date date of surgery completion + 1

Health economic data will be summarized using descriptive statistics by treatment group and overall, with Roll-ins presented in parallel.

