#### 5. POTENTIAL RISK/BENEFIT

#### 5.1 Potential Investigational Device Benefit

The observed and potential benefits of using CytoSorb® device intraoperatively during CPB in cardiac surgery:

- Reduction of free hemoglobin generated as a result of the CPB procedure
- Reduced inflammatory burden generated during the CPB procedure via reduction in C3a and C5a
- Potentially, a decrease in worsening renal function in subjects at significant risk
- Potentially, a reduction in vasopressor requirements
- Possible decrease in the amount of time on a mechanical ventilator
- Possible decrease in hospital stay, post CPB, including time in ICU
- Reduced risk of systemic inflammatory response syndrome (SIRS)

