#### 6.3.4 Secondary Effectiveness Endpoint(s)

Secondary effectiveness endpoints include the following:

- Change from baseline (defined as the start of CPB) in pfHb assessed hourly for the duration of CPB and at the end of CPB;
- Change from baseline (defined as start of CPB) in Complement 3a (C3a) assessed hourly for the duration of CPB and at the end of CPB;
- Severity of AKI through hospital discharge or post-surgical Day 7, whichever is sooner
- Incidence of AKI through hospital discharge or post-surgical Day 7, whichever is sooner
- Change from baseline (defined as pre-procedure) in serum creatinine through hospital discharge or post-surgical Day 7, whichever is sooner;

Additionally, the following pharmacoeconomic endpoints are included:

- Duration of hospital stay, post-surgery
- Duration of ICU stay, post-surgery
- Duration of renal replacement therapy, post-surgery
- Duration of vasopressor use, post-surgery
- Duration of ventilator use, post-surgery

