Operational notes (Surgery start & stop times, clamp times)			Х		X					
Adverse Events/SAEs			As	Needed (from	time ICF is	signed and su	bject is enrolled until s	study exit)		

 Within 14 days of surgery. If Screening is completed on the day of surgery, duplicate pre-procedure assessments/procedures do not need to be repeated.

 Daily, preferably at the same time each day.

 After approximately 5 minutes supine

 Randomization can be performed within 5 days prior to the cardiac surgery, but only after informed consent has been obtained.

 A minimum of 12 hours from time of admission to Post-Surgery Care Unit to the start of collection of data for daily is required.

 Echocardiogram for ejection fraction if an acceptable method (Section 6.4.1, Inclusion 3d) has not been completed within 90 days.

SOFA score will be assessed pre-procedure (before induction of anesthesia or sedation); on admission to post-surgical care; daily for 3 days post-procedure; and at Day 7 post-procedure or discharge, whichever occurs first). For post-surgical SOFA assessments, the lowest mean arterial pressure (MAP) from the day is used in the SOFA determination.

Vasopressor requirements: the maximum vasopressor dosage will be recorded each day (maximum dose over 1 hour).

 Vasopressors will be collected through day 7 if subject is still hospitalized.

 Blood transfusions will be collected through 30 days post cardiac surgery. Transfusion type (e.g. whole blood, packed red cells, platelets) will be recorded along with the volume administered

 Administration of fluids (crystalline) and supplementation with calcium and/or albumin begins at pre-procedure and will continue through the end of post-surgical Day 1. All administration and supplementation will be recorded. Following Day 1, administration of fluids and supplementation will be recorded as SOC until the point where the treating physician discontinues collection.

		Procedure (CPB/Surgery)						t-surgical pe	Discharge	Follow Up	

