6.8.1 Primary Safety Endpoint

The primary safety endpoint of this trial is to evaluate the product safety profile through the assessment of device related adverse events during the study period.

There is no formal hypothesis associated with the primary safety endpoint. Device related adverse events will be tabulated with the number of events and subjects with event for each MedDRA (Version 21.0) SOC/preferred term and overall. Rates will be reported as the number of subjects who experience at least one event out of the total number of subjects.

| Statistical Analysis Plan Pa | | ge 15 of 19 | |
|------------------------------|---|-------------|---------|
| Sponsor | Study | | Version |
| CytoSorbents | CYTOSORB [®] REDUCTION OF FREE HEMOGLOBIN/ACU INJURY (AKI) DURING CARDIAC SURGERY | te Kidney | 1.0 |

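### SAP 6.7.2.1 reports an undefined rate of vasopressor use in place of the protocol's secondary endpoint, the duration of vasopressor use

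*SAP*

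**What the plan says.** **Protocol.** Section 6.3.4 ends its list of secondary effectiveness endpoints with the line "Additionally, the following pharmacoeconomic endpoints are included". Five post-surgical durations follow: hospital stay, ICU stay, renal replacement therapy, vasopressor use and ventilator use. The fourth reads "Duration of vasopressor use, post-surgery", and the synopsis repeats it. Section 5.1 gives as a possible benefit "Potentially, a reduction in vasopressor requirements". On data, the footnotes to Table 3 say that "the maximum vasopressor dosage will be recorded each day (maximum dose over 1 hour"), and that collection continues to Day 7 while the subject is in hospital.

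**SAP.** Section 6.7.2.1 carries the same five items. Four stay durations with a formula, for example "Duration of renal replacement therapy post-surgery= End date of therapy" followed by the start date. The vasopressor item reads "Rate of vasopressor medication use post-surgery", with nothing further. The whole list is handled in one sentence: "Health economic data will be summarized using descriptive statistics by treatment group and overall, with Roll-ins presented in parallel". Section 6.7.2 puts secondary efficacy in the ITT population. Section 6.8.5 separately summarises vasopressor requirements to discharge or Day 7 in the safety population, without defining a duration.

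**The concern.** A duration and a rate answer different questions. The protocol's endpoint asks how long patients needed vasopressor support after surgery. A rate, if it means the share of patients with any use, asks only whether they needed it at all, so one day of support and seven days count the same.

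The protocol gives the question some weight. Besides the possible benefit in section 5.1, section 4 names vasoplegia as one of two inflammation-related complications of bypass with a substantial clinical burden. With the SAP followed as written, the final report would contain no vasopressor duration by randomised arm, and the reader would find no reason why this item alone among the five was changed.

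**Working it through.** The documents attach no sample size, effect size or power to this endpoint, so there is no planned figure to reproduce. The check is a comparison of the texts, followed by a short illustration.

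**1. The five items side by side.**

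| Item | Protocol 6.3.4 | SAP 6.7.2.1 |
|---|---|---|
| Hospital stay | Duration | Duration, with formula |
| ICU stay | Duration | Duration, with formula |
| Renal replacement therapy | Duration | Duration, with formula |
| Ventilator use | Duration | Duration, with formula |
| Vasopressor use | Duration | Rate, no definition |

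Only the vasopressor item differs in kind.

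**2. Is a duration computed elsewhere in the SAP?** Vasopressors appear again only in section 6.8.5. That section promises descriptive statistics on vasopressor requirements, and names neither a duration nor a count of days.

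**3. What does the rate mean?** Section 6.7.2.1 does not say. The only explicit definition in the SAP is for adverse events (6.8.1, with the same rule in 6.8.2.1 and 6.8.6): "Rates will be reported as the number of subjects who experience at least one event out of the total number of subjects". Carried over, it gives users divided by all subjects.

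**4. How does that quantity respond to shorter use?** The following figures are assumptions, since the documents give none for vasopressors. Let u be the share of users, the same in both arms, and let mean use among users be 4 days in one arm and 2 in the other.

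- Difference in rates = u − u = 0, whatever u is.
- Mean days over all subjects, with 0 for non-users = u × mean days among users.

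| Assumed u | Rate, both arms | Mean days, all subjects |
|---|---|---|
| 50% | 50% | 0.50 × 4 = 2.0 versus 0.50 × 2 = 1.0 |
| 80% | 80% | 0.80 × 4 = 3.2 versus 0.80 × 2 = 1.6 |
| 95% | 95% | 0.95 × 4 = 3.8 versus 0.95 × 2 = 1.9 |

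The rate moves only if some patients avoid vasopressors altogether. This follows from the definition and not from the values chosen.

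**5. Can a duration be derived?** Protocol 8.6.1 to 8.6.3 schedule vasopressor recording at admission to the post-surgical care unit and then through Days 1 to 7, and Table 3 adds the daily maximum dose. These give calendar days with any use, cut off at Day 7. They do not give start and stop times. The case report forms are not among the documents, so availability is inferred from the schedule.

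**The case against.** There is a fair case that this is a small matter, and several stronger readings should be resisted.

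- **That the rate cannot show a shorter need.** This assumes an ever/never rate. The SAP leaves the term undefined, and a per-day or person-time rate would partly reflect duration. What stands is that the item is undefined and does not match the protocol.
- **That the trial loses power.** A reader might set a test on ever-use against a test on days. The SAP plans no test for this item. Any such figures would also rest on assumed use and durations that the documents do not give. The same applies to an argument that the rate sits near its ceiling.
- **That the change was hidden.** SAP sections 1 and 4.1 say that the study stopped early and that analyses may depart from the protocol, so departures are disclosed in general terms. The notice neither lists nor explains this one. Early stopping also does not by itself explain changing one duration when four were kept.
- **That vasopressor data vanish from the report.** Section 6.8.5 does summarise them, and says that its items feed the health economic summary. If tabulated by day, that could hint at earlier weaning. But it is in the safety population, grouped under SAP 6.2 by treatment actually received, and its content is not defined.
- **That the endpoint can be restored exactly.** The protocol gives no formula for it. A count of days to Day 7 is a new, truncated variable. Without a rule for death, a patient who dies early would look like one who needed little support.

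**Conclusion.** The point holds as a mismatch between protocol and SAP that needs correcting. One of five pharmacoeconomic secondary endpoints is replaced by an undefined rate, with no stated reason and no vasopressor duration elsewhere in the SAP. On the natural reading, the replacement is insensitive to how long support lasts among patients who receive it.

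The consequence is limited. The endpoint is secondary and descriptive under the SAP, so no alpha, power, primary conclusion or safety conclusion changes. The conclusion about insensitivity rests on reading the rate as subjects with any use over all subjects. The mismatch itself rests on no assumption.

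**What to change.** In SAP 6.7.2.1, for the ITT population:

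- Add the number of post-surgical calendar days, from Day 0 to Day 7 or discharge, with any recorded vasopressor dose. Non-users score 0 and the maximum is 7 − 0 + 1 = 8 days. Count Day 0 from admission to the post-surgical care unit, so that use during bypass does not enter.
- Summarise it descriptively by arm, as for the four sibling durations.
- State that the count is truncated at Day 7.
- State how deaths before Day 7 are handled, so that early death does not count as short use. Either show them as a separate category or give them the maximum count.
- Say how a missed daily record is treated. SAP 6.3 imputes nothing, and a plain count would read a gap as a day without use.
- Keep the rate as a supporting row with its numerator and denominator stated.
- Record the departure from the protocol's endpoint, and the reason for it, in the SAP.

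The cost is one derived variable and a few lines of SAP text, with no new data collection if the scheduled daily records are in the database. The downside is the Day 7 truncation, which hides differences among patients supported for longer.

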6.8 Safety Analyses

Safety endpoints will be based on the Safety population.

For purposes of analyses relatedness to device or procedure will be defined as follows:

- An AE will be considered surgical procedure related if the relationship is definite, probable, possible, unrelated, or unknown.
- An AE will be considered investigational device related if the relationship is definite, probable, possible, unrelated, or unknown.

By-subject listings will be provided for all adverse events.

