### 8.8 Safety/Device Assessment

### 8.8.1 Adverse Events

Throughout the study, the Investigator or designee will determine adverse event (AE) occurrences. An adverse event is any untoward medical occurrence (signs, symptoms, abnormal laboratory findings) in a subject regardless of relationship to the device or procedure. Each adverse event is considered to be either anticipated or unanticipated as described below. AEs occurring after the initiation of treatment (start of CPB) are considered to be treatment emergent. The site is required to report the classes of Adverse Events that occur in the study, described below.

Any AEs and remedial action required will be recorded in the patient's source data. The nature, time of onset, duration, and severity will be documented, together with an Investigator's (or designee's) opinion of the relationship to investigational device. Since the incidence and severity of AKI, as defined by KDIGO clinical practice guidelines, are the primary endpoints of the study, the presence of AKI should not be reported as an AE in the trial.

If an AE occurs, appropriate diagnostic and therapeutic measures are to be taken. Follow-up evaluations of the patient are to be performed until the patient recovers or until the clinical Investigator considers the situation to be no longer clinically significant.

Adverse events are monitored and registered on the AE form of the eCRF at each visit. Whenever possible, a specific diagnosis should be entered as the AE term. Outcomes and severity of the AE are not to be recorded as the AE term. In absence of a specific diagnosis, an individual AE form has to be filled in for each sign or symptom. Changes from baseline laboratory values which are abnormal values and that are classified as clinically significant by the investigator must be recorded as AEs.

Persistent AEs will be entered once in the eCRF until they are resolved or if a new event has to be documented due to deterioration. These AEs will be carefully monitored. If an AE is still not resolved at the end of the investigation, this will be documented as ongoing.

For recurrent AEs (i.e., AEs of the same nature, but with a different date of onset), an individual AE form has to be completed for each of them.

Adverse events will be assessed for a relationship to each of the following and relationship classified as unrelated, possible, probable, definite or unknown:

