**Investigational Device Related Adverse Event:** An adverse event which, in the judgment of the Investigator, results as a consequence of the investigational device.

**Surgical Procedure Related Adverse Event:** An adverse event which, in the judgment of the Investigator, results as a consequence of the subject's surgical procedure and is not specific to the investigational device used.

**Non-Investigational Device Related Adverse Event:** An adverse event which, in the judgment of the Investigator, it is reasonable to believe that the event is associated with an accessory device used during the surgical procedure and is not specific to the investigational device use.

Grade 1	Mild:	Asymptomatic or mild symptoms; clinical or diagnostic observations only; intervention not indicated.
Grade 2	Moderate:	Minimal, local or noninvasive intervention indicated; limiting age-appropriate instrumental Activities of Daily Living (ADL)*.
Grade 3	Severe:	Severe or medically significant but not immediately life-threatening; hospitalization or prolongation of hospitalization indicated; disabling; limiting self-care ADL**.
Grade 4***	Life- threatening:	Life-threatening consequences; urgent intervention indicated.
Grade 5***	Death:	Death related to AE

Adverse events will also be evaluated for severity based on the following definitions:

\*Instrumental ADL refer to preparing meals, shopping for groceries or clothes, using the telephone, managing money, etc. \*\*Self-care ADL refer to bathing, dressing and undressing, feeding self, using the toilet, taking medications, and not bedridden. \*\*\*Adverse events that are assigned a severity of life-threatening or death will be recorded as Serious Adverse Events.

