### 11.1.1 Safety and Tolerability Evaluations:

The following analyses will be conducted on the Safety population and the two mITT subpopulations.

Continuous safety data will be summarized with descriptive statistics (arithmetic mean, standard deviation [SD], median, minimum, and maximum) by treatment group. Categorical safety data will be summarized with frequency counts and percent of patients by treatment group. Adverse events (AEs) will be coded using the most current Medical Dictionary for Regulatory Activities (MedDRA®) available. A by-participant AE data listing, including verbatim term, preferred term, system organ class, treatment, severity, and relationship to study device will be provided. The number and percent of participants experiencing procedure and device related AEs and serious AEs will be summarized by treatment group, system organ class, and preferred term.

Laboratory evaluations and vital signs assessments will be summarized by treatment group and protocol specified collection time point. A summary of change-from-baseline at each protocol specified time-point by treatment group will also be presented. "Shift Tables" will be provided to summarize count and percent of patients with changes from baseline normal range status (below, within, above) to on/post-treatment normal range status.

Further details regarding presentation and analysis of safety data will be detailed in the statistical analysis plan (SAP).

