6.8.2.2 Serious Device-related Adverse Events

The serious device-related adverse events in the study will be summarized similarly to the primary safety endpoint.

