6.8.6 Additional Safety

The total adverse events in the study will be summarized similarly to the primary safety endpoint. A summary will be presented by seriousness, severity, relationship to surgical procedure, relationship to investigational device, and relationship to non-investigational device will be provided using counts and percentage.

Non-serious adverse events will be tabulated with the number of events and subjects with event for each MedDRA SOC/preferred term and overall. Rates will be reported as the number of subjects who

| Statistical Analysis Plan Pa | | ge 17 of 19 | |
|------------------------------|---|-------------|---------|
| Sponsor | Study | | Version |
| CytoSorbents | CYTOSORB [®] REDUCTION OF FREE HEMOGLOBIN/ACU INJURY (AKI) DURING CARDIAC SURGERY | te Kidney | 1.0 |

experience at least one event out of the total number of subjects. Serious adverse events will be summarized in the same way.

Device deficiencies will be summarized by type of device observation in the safety population.

Subject deaths will be provided in listing format.

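### SAP 6.8 counts all five relationship codes, including 'unrelated', as related, so the primary safety table repeats the total adverse event table

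*SAP*

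**What the plan says.** Protocol 8.8.1 has each adverse event assessed against the investigational device, the surgical procedure and any accessory device, with the "relationship classified as unrelated, possible, probable, definite or unknown". The same section defines a device-related event as "An adverse event which, in the judgment of the Investigator, results as a consequence of the investigational device".

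SAP 6.8 then sets the definition to be used in the analysis. For the device: "An AE will be considered investigational device related if the relationship is definite, probable, possible, unrelated, or unknown". For the procedure: "An AE will be considered surgical procedure related if the relationship is definite, probable, possible, unrelated, or unknown".

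Four tabulations use these definitions:

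- SAP 6.8.1, the primary safety endpoint: device-related events by MedDRA system organ class and preferred term. The section adds: "There is no formal hypothesis associated with the primary safety endpoint".
- SAP 6.8.2.1: procedure-related events, by event type.
- SAP 6.8.2.1 again: serious procedure-related events.
- SAP 6.8.2.2: "The serious device-related adverse events in the study will be summarized similarly to the primary safety endpoint".

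SAP 6.8.6 separately plans a table of every event: "The total adverse events in the study will be summarized similarly to the primary safety endpoint". It treats all serious events in a like manner. It also plans counts and percentages by relationship category.

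Protocol 11.1.1 asks for subject counts and percentages, where those "experiencing procedure and device related AEs and serious AEs will be summarized by treatment group, system organ class, and preferred term".

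**The concern.** A relatedness rule exists to separate events attributed to the device from the background events of cardiac surgery. A rule that accepts 'unrelated' makes no such separation. It also contradicts the protocol, because an event the investigator rated unrelated cannot be one the investigator judged to be caused by the device.

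What is at stake is the designated primary safety result. If the table is programmed as specified, every coded adverse event appears under the label of device related, in the control arm as well, and a comparison of arms on that table is a comparison of all adverse events. The summary that Protocol 11.1.1 asks for, related events by arm, system organ class and preferred term, would appear in no planned table.

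The protocol's own background suggests the distinction is material. In the sponsor's earlier randomized trial (Protocol 2.1), device-related events involved 2 treated subjects (8.7%), and most adverse events were attributed to surgery or to pre-existing conditions. That does not predict the counts here, but it shows that the two sets of events can differ widely.

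**Working it through.** No sample size, power or alpha figure attaches to this point. The check is a comparison of two lists, then of the tables that depend on them.

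**Step 1. The codes.**

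| Code | Allowed by Protocol 8.8.1 | Counted as related by SAP 6.8 (device) | Counted as related by SAP 6.8 (procedure) |
|---|---|---|---|
| definite | yes | yes | yes |
| probable | yes | yes | yes |
| possible | yes | yes | yes |
| unknown | yes | yes | yes |
| unrelated | yes | yes | yes |

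Let P be the protocol's set (5 codes) and S the SAP's related set (5 codes). P minus S is empty and S minus P is empty, so the sets are identical. Codes excluded by the rule: 5 − 5 = 0. Every event with a recorded relationship passes.

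**Step 2. The tables.**

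| Tabulation | What it should isolate | What it selects as written |
|---|---|---|
| SAP 6.8.1 | device-related events | all coded events |
| SAP 6.8.2.1 | procedure-related events | all coded events |
| SAP 6.8.2.1, serious | serious procedure-related events | all coded serious events |
| SAP 6.8.2.2 | serious device-related events | all coded serious events |

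The count of affected tabulations is 1 + 2 + 1 = 4. The tables in 6.8.1 and 6.8.2.2 share both population and layout with the total and serious tables in 6.8.6, so each pair shows the same events. The two in 6.8.2.1 are laid out by event type, so they select the same events but need not look the same. The only possible difference is an event whose relationship field is blank; SAP 6.3 does not impute, so such an event would drop out of the related tables.

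**Step 3. The control arm.** Protocol 8.8.1 has adverse events assessed for relationship to the device and makes no exception by arm. A control subject's event coded 'unrelated' to the device is therefore counted as device related.

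**Step 4. Extent.** The Safety population is the roll-in and randomized subjects in whom treatment was attempted (SAP 6.2). It cannot exceed the 151 enrolled (SAP 4.1). The over-count in each table equals the number of events in its scope rated 'unrelated', which the documents do not give.

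**Step 5. After correction.** Dropping 'unrelated' keeps 4 of 5 codes and excludes 1. Dropping 'unknown' as well would keep 3 of 5. Either version separates the device-related table from the total table.

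**The case against.** The strongest reply is that this is a drafting slip with little consequence. The SAP plans separate tables for related and for total events, and a summary by relationship category. None of that would make sense if every event were related, so the literal reading is plainly not the intent. The endpoint is descriptive, so no test is affected. No data are lost: Protocol 11.1.1 calls for a by-participant listing with preferred term, system organ class, treatment and relationship, and SAP 6.8 keeps by-subject listings of all events. If those listings carry the protocol's columns, the whole correct table can be rebuilt. The error also inflates the device-related count, so it would not conceal events, although it could dilute a signal among background events.

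Most of this is fair and limits the harm. It does not remove the defect. The wording is introduced as the definition for analysis, appears twice, and is corrected nowhere. With no hypothesis test, the table itself is the primary safety result, and a reader should not have to reconstruct it from listings. A programmer who put it right silently would be departing from the SAP, whose section 7 asks for changes to be documented in an amendment, approved before analysis when possible. Early termination explains a reduced set of analyses, but gives no reason to count unrelated events as related.

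A second objection concerns 'unknown'. An event of unknown relationship has not been judged a consequence of the device, so keeping that code still falls short of the protocol's definition and could leave some control-arm events in the table. That stands as a matter for the sponsor to decide and explain.

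**Conclusion.** The concern holds and should be corrected before analysis. As written, the rule excludes 0 of 5 codes, four tabulations lose their meaning, and no planned table by system organ class and preferred term isolates device-related events, which are the primary safety endpoint.

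The damage is bounded. Efficacy, type I error and power are unaffected, the population is at most 151 subjects, and overall counts by relationship remain available from the category summary in SAP 6.8.6. The conclusion assumes only that the SAP is programmed as written and that the relationship field is completed with the protocol's codes. No claim is made about the size of the over-count.

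**What to change.** In SAP 6.8, delete 'unrelated' from both bullets, so that related means definite, probable, possible or unknown. Add one sentence saying that events rated unrelated are not counted as related, and apply it to 6.8.1, 6.8.2.1 and 6.8.2.2.

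The SAP already counts 'unknown' as related, and this change leaves that in place. The documents give no reason for it, so the sponsor should state in its own words how 'unknown' is handled and why. No new rule is needed for a blank field; SAP 6.3 continues to apply.

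The cost is one word deleted in each of two bullets, the clarifying sentences and a change to the table filter. No new data are required.
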